APPENDIX V: PATIENT INSTRUCTIONS FOR TREATING DIARRHEA

Guidelines for the Treatment of Diarrhea

Institutional practice may be used in place of these guidelines.

You should purchase or will be given a prescription for loperamide to have available to begin treatment at the first episode of poorly formed or loose stools or the earliest onset of bowel movements more frequent than normally expected for the patient. Patients will also be instructed to contact their physician if any diarrhea occurs. Patients will be given **loperamide** based on body weight.

Early diarrhea

Early onset diarrhea associated with irinotecan is usually preceded by sweating and abdominal cramping. Patients who have the onset of these symptoms followed by diarrhea within several hours after taking irinotecan should contact the treating physician immediately. The treating physician may consider treatment with atropine. If symptoms do not improve with administration of atropine, treatment for late diarrhea (as outlined below) should be started.

Late diarrhea (more than 24 hours after the administration of the first dose of irinotecan)

Each family will be instructed to have antidiarrheal medication available and begin treatment at the first episode of poorly formed or loose stools or the earliest onset of bowel movements more frequent than normally expected for the patient. Patients will also be instructed to contact their physician if any diarrhea occurs. Patients will be given loperamide based on body weight.

Be aware of your child's bowel movements. At the first sign they become softer than usual or if your child has any notable increase in the number of bowel movements over what is normal for him/her, begin taking loperamide (Imodium). **If he/she does not start taking the loperamide right away, the diarrhea may become severe and last several days or require hospitalization.**

Please follow these directions carefully, using dosing guidelines below:

- Take _____ at the first sign of diarrhea.
- Continue taking _____ every _____ hours until the diarrhea slows or the normal pattern of bowel movements returns. Repeat the same doses and frequency if the diarrhea returns.
- Do not exceed _____ in a 24 hour period.
- Please call your doctor if you have any questions about taking loperamide, if your child's diarrhea is not under control after two days, or if he/she is feeling extremely weak, lightheaded, or dizzy.
- Make an extra effort to give your child lots of fluids (several glasses of pedialyte, fruit juices, soda, soup, etc.) while your child is participating in this study.
- Side effects may include tiredness, drowsiness or dizziness. If your child experiences these side effects, or if your child is urinating less frequently than usual, please contact your child's physician.
- Do not give your child any laxatives without consulting with his/her physician.

LOPERAMIDE DOSING RECOMMENDATIONS FOR LATE DIARRHEA

(maximum dose of loperamide for adults is 16 mg/day)

ALL patients: discontinue loperamide when the patient is no longer experiencing significant diarrhea.

Weight (kg)	ACTION
<13 kg	Take 0.5 mg (one-half teaspoonful of the 1 mg/5 mL oral solution) after the first loose bowel movement, followed by 0.5 mg (one-half teaspoonful of the 1 mg/5 mL oral solution) every 3 hours. During the night, the patient may take 0.5 mg (one-half teaspoonful of the 1 mg/5 mL oral solution) every 4 hours. Do not exceed 4 mg per day (20 mL or 4 teaspoonfuls) per day.
≥ 13 kg to < 20 kg	Take 1 mg (1 teaspoonful of the 1 mg/5 mL oral solution or one-half tablet) after the first loose bowel movement, followed by 1 mg (one teaspoonful of the 1 mg/5 mL oral solution or one-half tablet) every 3 hours. During the night, the patient may take 1 mg (one teaspoonful of the 1 mg/5 mL oral solution or one-half tablet) every 4 hours. Do not exceed 6 mg per day (30 mL or 6 teaspoonfuls) per day.
≥ 20 kg to < 30 kg	Take 2 mg (2 teaspoonfuls of the 1 mg/5 mL oral solution or 1 tablet) after the first loose bowel movement, followed by 1 mg (one teaspoonful of the 1 mg/5 mL oral solution or one-half tablet) every 3 hours. During the night, the patient may take 2 mg (2 teaspoonfuls of the 1 mg/5 mL oral solution or 1 tablet) every 4 hours. Do not exceed 8 mg per day (40 mL or 8 teaspoonfuls) per day.
≥ 30 kg to < 43 kg	Take 2 mg (2 teaspoonfuls of the 1 mg/5 mL oral solution or 1 tablet) after the first loose bowel movement, followed by 1 mg (one teaspoonful of the 1 mg/5 mL oral solution or one-half tablet) every 2 hours. During the night, the patient may take 2 mg (2 teaspoonfuls of the 1 mg/5 mL oral solution or 1 tablet) every 4 hours. Do not exceed 12 mg per day (60 mL or 12 teaspoonfuls) per day.
Over 43 kg	Take 4 mg (4 teaspoonfuls of the 1 mg/5 mL oral solution or 2 capsules or tablets) after the first loose bowel movement, followed by 2 mg (2 teaspoonfuls of the 1 mg/5 mL oral solution or 1 capsule or tablet) every 2 hours. During the night, the patient may take 4 mg (4 teaspoonfuls of the 1 mg/5 mL oral solution or 2 capsules or tablets) every 4 hours. Do not exceed 16 mg per day (80 mL or 16 teaspoonfuls) per day.

APPENDIX VI: TEMOZOLOMIDE DOSING (100 mg/m²) NOMOGRAM

Temozolomide is dosed based on body surface area for patients whose BSA is at least 0.5 m². For these patients, doses are rounded to the nearest 5 mg. For patients with BSA < 0.5 m², dosing is based on body weight (kg).

For patients with a BSA < 0.5 m²: Use **3.3 mg/kg**.

Examples: For a patient with BSA= 0.3 m² and weight= 5 kg, the calculated dose = 5 kg x 3.3 mg/kg = 16.5 mg

Temozolomide oral suspension is compounded to a concentration of 10 mg/mL. When temozolomide suspension is used, consider rounding doses to the nearest 1 mg (0.1 mL) for doses \leq 22.5 mg and to the nearest 2 mg (0.2 mL) for doses $>$ 22.5 mg for deliverability. In the example above, the dose can be rounded to 16 mg (1.6 mL).

For a patient with BSA= 0.66 m² the calculated dose is $0.66 \text{ m}^2 \times 100 \text{ mg/m}^2 = 66 \text{ mg/day}$; administered dose = 65 mg temozolomide/day.

BSA (m ²)	Calculated daily dose (mg)	Administered daily dose (mg)
0.2-0.49	3.3 mg/kg	3.3 mg/kg
0.50-0.52	50-52	50
0.53-0.57	53-57	55
0.58-0.62	58-62	60
0.63-0.67	63-67	65
0.68-0.72	68-72	70
0.73-0.77	73-77	75
0.78-0.82	78-82	80
0.83-0.87	83-87	85
0.88-0.92	88-92	90
0.93-0.97	93-97	95
0.98-1.0	98-100	100
1.01-1.05	100-105	105
1.06-1.14	106-114	110
1.15-1.24	115-124	120
1.25-1.34	125-134	130
1.35-1.44	135-144	140
1.45-1.54	145-154	150
1.55-1.64	155-164	160
1.65-1.74	165-174	170
1.75-1.84	175-184	180
1.85-1.94	185-194	190
1.95-2.00	195-200	200
> 2.0	> 200	200

APPENDIX VII: TEMOZOLOLIMIDE REDUCED (75 mg/m²) DOSING NOMOGRAM

Temozolomide is dosed based on body surface area for patients whose BSA is at least 0.5 m². For these patients, doses are rounded to the nearest 5 mg. For patients with BSA < 0.5 m², dosing is based on body weight (kg).

For patients with a BSA < 0.5 m²: Use **2.5 mg/kg**.

Examples: For a patient that is 0.3 m² and weighs 5 kg, the calculated dose is 5 kg x 2.5 mg/kg = 12.5 mg

Temozolomide oral suspension is compounded to a concentration of 10 mg/mL. When temozolomide suspension is used, consider rounding doses to the nearest 1 mg (0.1 mL) for doses \leq 22.5 mg and to the nearest 2 mg (0.2 mL) for doses $>$ 22.5 mg for deliverability. In the example above, the dose can be rounded to 12 mg (1.2 mL).

For a patient with a BSA of 0.66 m², the calculated dose = 49.5 mg/dose; administered dose = 50 mg temozolomide/dose.

BSA (m ²)	Calculated daily dose (mg)	Administered daily dose (mg)
0.2-0.49	2.5 mg/kg	2.5 mg/kg
0.50-0.56	38-42	40
0.57-0.63	43-47	45
0.64-0.70	48-52	50
0.71-0.76	53-57	55
0.77-0.83	58-62	60
0.84-0.90	63-67	65
0.91-0.96	68-72	70
0.97-1.03	73-77	75
1.04-1.10	78-82	80
1.11-1.16	83-87	85
1.17-1.23	88-92	90
1.24-1.30	93-97	95
1.31-1.36	98-102	100
1.37-1.43	103-107	105
1.44-1.50	108-112	110
1.51-1.56	113-117	115
1.57-1.63	118-122	120
1.64-1.70	123-127	125
1.71-1.76	128-132	130
1.77-1.83	133-137	135
1.84-1.90	138-142	140
1.91-1.96	143-147	145
≥ 1.97	148-152	150

APPENDIX VIII: INSTRUCTIONS FOR TEMOZOLOMIDE PREPARATION, ADMINISTRATION AND SAFE HANDLING

Patient Name: _____

Cycle#: _____ Date Range: _____

Temozolomide is an oral medicine for the treatment of cancer. This information sheet will help you prepare, administer, store, and dispose of the medicine. Please read the information before preparing and giving the medicine. If you have any questions, please contact: _____

WHAT DO I NEED?

Your **Temozolomide** dose is: _____ mg

- You should use the following number of capsules for each dose:

Number of temozolomide capsules per dose					
5 mg	20 mg	100 mg	140 mg	180 mg	250 mg

- Give each dose by mouth one time each morning for 5 days in a row.
- You should take the temozolomide on the following days: _____

Supplies:

- Temozolomide capsules (see the table above)
- Disposable pad or paper towels
- Disposable gloves and mask and a pair of goggles (eye protection)
- Disposable cup and disposable spoon
- A container to collect waste (zip top plastic bag or medical waste bag or container)
- A small amount of applesauce or apple juice
 - Two teaspoons (10 mL) should be enough. A single-serving container of applesauce may be used, but the patient must be able to eat the entire contents of the container to ensure the full dose is taken.
 - Food should be cool or close to room temperature when administered; do not use hot or boiling food

HOW DO I STORE THE MEDICINE AND WASTE?

Store the medication in the original bottle away from food and out of the reach of children or pets. Store the waste container out of the reach of children or pets. Return the container to the clinic during your next visit.

WHAT SAFETY MEASURES SHOULD I TAKE?

If the medicine gets into eyes, hold eyelids open while flushing with water for at least 15 minutes. If you spilled the medicine on your skin, remove contaminated clothing. Wash area with soap and large amount of water. Seek medical attention if the skin becomes red, irritated, or if you are concerned. Call your doctor or nurse immediately at: _____

and/or contact the Poison Center at [name].

HOW DO I PREPARE THE MEDICINE?

CAUTION: If you are pregnant, could become pregnant, or are breast-feeding, DO NOT prepare or administer this medicine.

1. Choose a quiet working space away from food, windows, fans or heat ducts.
2. Clean the working space with damp paper towels.
3. Wash your hands with soap and water; dry them well.
4. Put on disposable gloves, disposable mask, and a pair of goggles or eye protection.
5. Place a disposable pad or paper towel on the clean working space and place all supplies on the pad or paper towel.
6. Fill a cup with a small amount of apple juice or applesauce (or use pre-filled applesauce cup).
7. Open each capsule required for the daily dose over the cup with the apple juice or applesauce.
 - Hold one capsule over the center of the cup.
 - To open, pinch both ends of one capsule with gentle pressure. Slowly rotate one end in small, back and forth movements while holding the other end steady until the capsule sections begin to separate.
 - Gently separate the ends so the powder falls into the center of the food. Look inside each end of the capsule. Tap and shake each end of the capsule until all medicine powder is out of the capsule.
 - Repeat the steps above for each capsule needed.
8. The medicine will not dissolve completely if mixing in apple juice. Keep extra apple juice on hand to add to any remaining powder left at the bottom of the cup. If you need more apple juice or applesauce, remove your gloves before touching the main container. Wear new gloves before adding the additional apple juice or applesauce to the medicine to prevent contaminating the main container with any powder that may be on your gloves.
9. Give the medicine mixture to the patient immediately.

HOW DO I TAKE/GIVE THE MEDICINE?

- Take/give an anti-nausea medicine 30-60 minutes before the temozolomide only if instructed to do so by your doctor.
- Take/give temozolomide 1 hour before irinotecan.
- Take/give temozolomide at around the same time each day with or without food. On days where you have special blood tests drawn, take both medicines on an empty stomach, at least 2 hours after food.
- When you are finished, place all used supplies in a plastic zip top bag or the waste container that was provided to you by your doctor, nurse, or pharmacist.
- If the dose is vomited within 30 minutes, the dose should be repeated. If the dose is vomited more than 30 minutes after the dose, do not repeat the dose. If the patient is unable to take a dose, or a dose is accidentally missed, place the remaining medicine from this dose in the waste container, seal, and contact your doctor or nurse for instructions.

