4.4.3 Treatment Details for Regimen A Cycle 1 (3 weeks = 1 cycle)

Drug doses should be calculated based on the BSA using height and weight obtained within 1 week prior to the beginning of each cycle.

Suggested administration schedule for chemotherapy and dinutuximab (Days 2-5):

- At hour 0: patient should receive oral temozolomide.
- At hour 1: patient should start IV irinotecan over 90 minutes, and on days patient is receiving dinutuximab infusion (Days 2-5 of each cycle), start IVF bolus of normal saline (10-20 mL/kg) over 1 hour.
- At hour 2.5: on days patient is receiving dinutuximab infusion (Days 2-5 of each cycle), start dinutuximab infusion.

Temozolomide: PO daily (NG or G-tube administration is allowed)

Days: 1-5

Dose: Round doses to the nearest 5 mg when using capsules. See dosing table in [Appendix VI](#).

For patients $\geq 0.5 \text{ m}^2$: 100 mg/ m^2/dose

For patients $< 0.5 \text{ m}^2$: 3.3 mg/ kg/dose

MAX dose = 200 mg

Substitution of IV Temozolomide is not permitted.

Sequencing: when giving with irinotecan, administer temozolomide first and wait 1 hour before giving irinotecan.

Absorption is affected by food and therefore, consistency of administration with respect to food is suggested. Preferably, administer on an empty stomach (at least 1 hour before or 2 hours after food) to decrease nausea and vomiting and improve absorption. The whole dose, even if comprised of several capsule sizes, should be taken at one time at approximately the same time each day. Antiemetics are recommended to prevent nausea and vomiting. When using temozolomide capsules, the dose should be rounded to the nearest 5 mg (round 2.5 mg down, see [Appendix VI](#)). For ease of swallowing, the capsule content may be mixed with applesauce or apple juice. An oral suspension may also be compounded by a pharmacist. If emesis occurs within 20 minutes of taking a dose of temozolomide, then the dose should be repeated once. If emesis occurs after 20 min, the dose should not be repeated.

Administration of oral temozolomide should be documented; missed doses should be noted on therapy delivery map and/or in accordance with institutional policy/procedures.

Special precautions: Temozolomide capsules are available in 6 different strengths. Daily doses are usually comprised of multiple capsules of different strengths. To prevent errors, each strength of temozolomide capsules must be dispensed in a separate bottle and the total number of each strength of capsules

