Absorption is affected by food and therefore, consistency of administration with respect to food is suggested. Preferably, administer on an empty stomach (at least 1 hour before or 2 hours after food) to decrease nausea and vomiting and improve absorption. The whole dose, even if comprised of several capsule sizes, should be taken at one time at approximately the same time each day. Antiemetics are recommended to prevent nausea and vomiting. When using temozolomide dose capsules, the dose should be rounded to the nearest 5 mg (round 2.5 mg down, see [Appendix VI](#)). For ease of swallowing, the capsule content may be mixed with applesauce or apple juice. An oral suspension may also be compounded by a pharmacist.

If emesis occurs within 20 minutes of taking a dose of temozolomide, then the dose should be repeated once. If emesis occurs after 20 minutes, the dose should not be repeated.

Administration of oral temozolomide should be documented; missed doses should be noted on therapy delivery map and/or in accordance with institutional policy/procedures

Special precautions: Temozolomide capsules are available in 6 different strengths. Daily doses are usually comprised of multiple capsules of different strengths. To prevent errors, each strength of temozolomide capsules must be dispensed in a separate bottle and the total number of each strength of capsules needed for the full course must be dispensed at one time. See [Section 6.5](#) for additional details and examples.

Irinotecan: IV over 90 minutes daily

Days: 1-5

Dose: 50 mg/m²/dose (regardless of BSA)

Note: Irinotecan should be administered at least 1 hour after the temozolomide has been given.

Higher incidence of cholinergic symptoms has been reported with more rapid infusion rates.

See the Parenteral Chemotherapy Administration Guidelines (CAG) for special precautions and suggestions for patient monitoring on the COG website at:

https://www.cogmembers.org/_files/disc/Pharmacy/ChemoAdminGuidelines.pdf

Dinutuximab: IV over 10 hours* daily

Days: 2-5

Dose: 17.5 mg/m²/dose

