6.5 TEMOZOLOMIDE (08/26/20)
(Temodar[®], Temodal[®]) NSC #362856

Source and Pharmacology:

An orally or intravenously administered alkylating agent, a second generation imidazotetrazine. A prodrug of MTIC, temozolomide spontaneously decomposes to MTIC at physiologic pH.

The cytotoxic effects of MTIC are manifested through alkylation (methylation) of DNA at the O⁶, N⁷ guanine positions which lead to DNA double strand breaks and apoptosis. Temozolomide is noncell cycle specific.

Temozolomide is rapidly and completely absorbed after oral administration with a peak plasma concentration (C_{max}) achieved in a median T_{max} of 1 hour. Food reduces the rate and extent of temozolomide absorption. Mean peak plasma concentration and AUC decreased by 32% and 9%, respectively, and median T_{max} increased by 2-fold (from 1-2.25 hours) when temozolomide was administered after a modified high-fat breakfast. A pharmacokinetic study comparing oral and intravenous temozolomide in patients with primary CNS malignancies showed that at 150 mg/m² dose temozolomide IV and oral capsules are bioequivalent with respect to both C_{max} and AUC of temozolomide and MTIC. Temozolomide has a mean apparent volume of distribution of 0.4 L/kg (%CV=13%). It is weakly bound to human plasma proteins; the mean percent bound of drug-related total radioactivity is 15%. Temozolomide is spontaneously hydrolyzed at physiologic pH to the active species, MTIC and to temozolomide acid metabolite. Cytochrome P450 enzymes play only a minor role in the metabolism of temozolomide and MTIC. About 38% of the administered temozolomide total radioactive dose is recovered in the urine. Overall clearance of temozolomide is about 5.5 L/hr/m². Temozolomide is rapidly eliminated, with a mean elimination half-life of 1.8 hours, and exhibits linear kinetics over the therapeutic dosing range of 75 to 250 mg/m²/day. A population analysis did not demonstrate any influence of coadministered dexamethasone, prochlorperazine, phenytoin, carbamazepine, ondansetron, H₂ receptor antagonists, or phenobarbital on the clearance of orally administered temozolomide.

The table below lists the anticipated toxicity profile of temozolomide (oral):

Incidence	Toxicities
Common (>20% of patients)	Constipation, nausea, vomiting, , anorexia, alopecia, headache, seizure, fatigue

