Occasional (4-20% of patients)	Peripheral edema, skin rash, pruritus, xeroderma, erythema of skin, diarrhea, dysphagia, dizziness, ataxia, hemiparesis, asthenia, fever, stomatitis, abdominal pain, dysgeusia, weight gain, platelet count decreased, white blood cell count decreased, lymphocyte count decreased, urinary incontinence or frequency, cough, dyspnea, infection, anxiety, depression, insomnia, gait disturbance, amnesia, paresthesia, drowsiness, visual disturbances, back pain, arthralgia/myalgia
Rare (≤3% of patients)	Stevens-Johnson syndrome, toxic epidermal necrolysis, erythema multiforme, hyperbilirubinemia, transaminitis, injection site reaction (IV formulation), interstitial pneumonitis, pancytopenia (may be prolonged), myelodysplastic syndrome, leukemia secondary to oncology chemotherapy, infections and infestations – other: Pneumocystis pneumonia, pulmonary fibrosis, anaphylaxis, allergic reaction, hepatotoxicity, cholestasis, anemia, aplastic anemia
Pregnancy & Lactation	
Pregnancy Category D
 
Adequate, well-controlled studies have not been conducted in humans. Women of childbearing potential should be advised against becoming pregnant while taking temozolomide and for at least 6 months following the end of therapy. Temozolomide administration to rats and rabbits at 3/8 and 3/4 the human dose resulted in the development of malformations of the external organs, soft tissues, and skeleton. These animal studies also demonstrated embryo lethality (increased resorptions) at similar doses. There is no information available regarding the transmission of temozolomide during lactation; women should avoid breastfeeding while receiving temozolomide.

Formulation and Stability:

Temozolomide capsules are available in six different strengths (5, 20, 100, 140, 180, 250 mg). The capsules vary in size, color, and imprint according to strength. In the US, capsules are packaged in 5-count and 14-count bottles. In other countries temozolomide may be packaged in 5-count, 14-count or 20-count bottles. Temozolomide capsules are stored at 25°C (77°F); excursions permitted to 15°C to 30°C (59°F to 86°F).

Guidelines for Administration:

See Treatment and Dose Modifications sections of the protocol.

There is a potential for medication errors involving temozolomide capsules resulting in drug overdosages, which may have been caused by dispensing/taking the wrong number of capsules per day and/or product usage exceeding the prescribed dosing schedule.

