When dispensing, it is extremely important that prescribing and dispensing include clear instructions on which capsules, and how many of each capsule(s) are to be taken per day. Only dispense what is needed for the course, and clearly indicate how many days of dosing the patient will have and how many days are without temozolomide dosing. When counseling patients, it is important for each patient/parent to understand the number of capsules per day and the number of days that they take temozolomide. It is also important for the patient/parent to understand the number of days that they will be off the medication.

Each strength of temozolomide must be dispensed in a separate vial or in its original container (e.g., bottle or sachet). Based on the dose prescribed, determine the number of

each strength of temozolomide capsules needed for the full course as prescribed by the physician. For example, 275 mg/day for 5 days would be dispensed as five 250 mg capsules, five 20 mg capsules, and five 5 mg capsules. Label each container with the appropriate number of capsules to be taken each day. Dispense to the patient/parent, making sure each container lists the strength (mg) per capsule and that he or she understands to take the appropriate number of capsules of temozolomide from each bottle or vial to equal the total daily dose prescribed by the physician. Institutions that have the capability to dispense temozolomide as daily doses in a blister pack may do so, taking specific precautions to ensure that the appropriate dose is provided and that the patient is educated to understand the daily dosing regimen.

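### The temozolomide family sheet directs a repeat dose after vomiting up to 30 minutes; the treatment sections say not to repeat after 20 minutes

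*Combined protocol and SAP*

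**What the plan says.** The temozolomide paragraphs of all four treatment sections (4.4.3 and 4.5.3 for Regimen A, 4.6.3 and 4.7.3 for Regimen B) carry the same rule. Section 4.4.3 puts it this way: "If emesis occurs within 20 minutes of taking a dose of temozolomide, then the dose should be repeated once". Section 4.5.3 closes the window: "If emesis occurs after 20 minutes, the dose should not be repeated". The other sections do the same in near-identical words.

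Appendix VIII is addressed to the person who prepares and gives the drug at home. It says: "If the dose is vomited within 30 minutes, the dose should be repeated". It then adds: "If the dose is vomited more than 30 minutes after the dose, do not repeat the dose". It does not say that the repeat is to be given only once, although its general direction is "Give each dose by mouth one time each morning for 5 days in a row".

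Section 6.5, the temozolomide drug information, contains no rule on vomiting. It does warn: "There is a potential for medication errors involving temozolomide capsules resulting in drug overdosages". It also describes absorption: "Temozolomide is rapidly and completely absorbed after oral administration with a peak plasma concentration", with the median peak at 1 hour.

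**The concern.** A dosing rule that appears in five places should be the same in all of them. Here the four places written for clinicians agree, and the one written for families differs. A family holding the sheet has no reason to look up Section 4. The sheet's prompt to call the clinic covers doses that cannot be taken or are missed, not doses that are vomited.

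What is at stake is one additional full dose of an alkylating agent on a day when the treatment sections say none should be given. Section 6.5 puts the median peak at 1 hour, so part of a dose vomited at 20 to 30 minutes may already have been absorbed. Temozolomide is also the drug that Sections 5.1.1 and 5.1.2 reduce by 25% for prolonged neutropenia or thrombocytopenia.

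The protocol anticipates the situation. Vomiting is listed among the common toxicities (over 20% of patients) of both temozolomide and irinotecan. The Regimen B text suggests giving eflornithine and temozolomide close together on Days 1-5 to limit vomiting and re-dosing. A Regimen B family may then hold two sheets with different windows: Appendix XIII uses 20 minutes and one repeat for eflornithine. If both drugs are given together and the child vomits at 25 minutes, one sheet says repeat and the other says do not.

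**Working it through.** **Step 1. Set the rules side by side.**

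| Time of vomiting after the dose | Sections 4.4.3, 4.5.3, 4.6.3, 4.7.3 | Appendix VIII |
|---|---|---|
| Within 20 minutes | Repeat, once | Repeat; number of repeats not stated |
| After 20 and up to 30 minutes | Do not repeat | Repeat |
| More than 30 minutes | Do not repeat | Do not repeat |

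The instructions are opposite only in the middle row. Its width is 30 − 20 = 10 minutes.

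**Step 2. Decide which text is the outlier.** The 20-minute rule with one repeat is in all four temozolomide treatment paragraphs. It is also the eflornithine rule in Sections 4.6.3 and 4.7.3 and in Appendix XIII. The 30-minute rule appears only in Appendix VIII.

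**Step 3. Size the difference on one day.** Inputs:

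- planned daily dose d: 100 mg/m² at a BSA of 0.5 m² or more, 3.3 mg/kg below that, maximum 200 mg (Section 4.4.3 and Appendix VI); 75 mg/m² after a dose reduction (Appendix VII);
- share f of the first dose that is vomited: not given in the documents, so taken over its whole range, 0 to 1;
- one repeat, fully retained.

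For vomiting at 20 to 30 minutes:

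- retained under Section 4: d × (1 − f);
- retained under Appendix VIII: d × (1 − f) + d;
- difference: d, whatever the value of f.

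| Planned dose d | Section 4: f = 0 / 0.5 / 1 | Appendix VIII: f = 0 / 0.5 / 1 | Difference |
|---|---|---|---|
| 100 mg/m² | 100 / 50 / 0 | 200 / 150 / 100 | 100 mg/m² |
| 75 mg/m² (reduced) | 75 / 37.5 / 0 | 150 / 112.5 / 75 | 75 mg/m² |
| 200 mg (cap) | 200 / 100 / 0 | 400 / 300 / 200 | 200 mg |
| 3.3 mg/kg (BSA below 0.5 m²) | 3.3 / 1.65 / 0 | 6.6 / 4.95 / 3.3 | 3.3 mg/kg |

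The largest value under the sheet is 2d, or 200% of the planned daily dose. It requires f = 0, meaning that nothing of the first dose was lost. The cap row applies only from a BSA of 1.95 m² (Appendix VI).

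**Step 4. Compare with what Section 4 already accepts.** For vomiting within 20 minutes, Section 4 also directs one repeat, so the same formula d × (1 − f) + d applies and the range is again 200 down to 100 mg/m². The sheet therefore does not create a larger one-day maximum than the protocol tolerates. It extends by 10 minutes the period in which that amount can arise, into a period when more of the first dose may have been absorbed.

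**The case against.** The mismatch is not in dispute; its weight is. The strongest points on the other side are these.

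- **Narrow window and unknown frequency.** Only vomiting at 20 to 30 minutes is affected, and the documents give no rate for it. This stands.
- **Limited reach.** Section 6.5 cites Appendix VIII only for capsules opened into apple sauce or juice. Sections 4.6.3 and 4.7.3 ask sites to hand the eflornithine instructions to families, but no such request is made for the temozolomide sheet. Irinotecan on Days 1-5 and dinutuximab on Days 2-5 bring staff contact on every temozolomide day, so staff may often decide on re-dosing. This stands as a limit on how often the sheet governs. It does not make the sheet correct.
- **The 200% figure is not peculiar to the sheet.** Correct, as Step 4 shows. The difference of one full dose inside the window is unchanged.
- **The dose is within the range quoted for the drug.** 200 mg/m² lies inside the 75 to 250 mg/m²/day that Section 6.5 gives for temozolomide in general. True, but the planned dose here is 100 mg/m², given with irinotecan and dinutuximab.
- **Harm is not shown.** The Section 6.5 overdose warning concerns wrong capsule numbers or use beyond the schedule, not re-dosing after vomiting. Food delays the median peak from 1 to 2.25 hours, and the sheet allows dosing with food. The amount absorbed by 20 to 30 minutes is not stated. So harm is possible but unquantified.
- **Supply is limited.** Section 6.5 directs "Only dispense what is needed for the course", so an excess over the whole cycle does not follow. None is claimed.

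No part of this reconciles the two texts or argues for keeping 30 minutes.

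**Conclusion.** The inconsistency is real and is in current text. For vomiting after 20 and up to 30 minutes, Appendix VIII directs a repeat that the four treatment sections say should not be given, so a site or family cannot comply with both. The difference is one full daily dose in that window: 100 mg/m², 75 mg/m² after reduction, 3.3 mg/kg below 0.5 m², or 200 mg at the cap. The range of retained amounts rests on two assumptions: that 0% to 100% of the first dose is vomited, and that one repeat is given and kept down.

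The missing limit to one repeat in Appendix VIII is a smaller gap. The singular wording and the once-each-morning direction point to one repeat, so the sheet should not be read as permitting unlimited repeats.

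This is a safety and consistency point about dosing. The text is common to both arms, and nothing here bears on type I error, power or the response comparison. It should be corrected because it is an operative instruction for an oral cytotoxic in a mainly paediatric trial.

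**What to change.** Replace the two sentences on vomiting in Appendix VIII with wording that matches Section 4 and Appendix XIII. Suggested text: *If the dose is vomited within 20 minutes, repeat the dose once. If it is vomited after 20 minutes, do not repeat the dose.* Re-issue the family sheet to sites so that copies with the 30-minute rule are withdrawn.

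The cost is two sentences at the next amendment plus redistribution of the sheet. There is no change to the design, sample size, data collection or analysis.
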